8.7.1.2.5 Primary and Secondary Endpoints

Analysis of primary efficacy endpoint

The primary endpoint of this trial is a composite of all cause-death or any use of invasive mechanical ventilation up to 28 days or hospital discharge.

Invasive mechanical ventilation is defined as patients who are intubated or have a tracheostomy tube and are receiving positive pressure ventilation. Patients who will be discharged from hospital before day 28 will be considered as non-event after confirmation by telephone interview that they are alive at day 28. Patients who will be discharged from hospital or early terminated before Day 28 will be considered having an event on the day of discharge or early termination, if a telephone interview was not possible and/or no information about alive/death status is known.

Hypothesis to be tested:

H0: $p_{APN01} = p_{Placebo}$

H1: $p_{APN01} \neq p_{Placebo}$

H0 will be tested using a Chi-squared test. The level of significance is 5% (two-sided). In addition, logistic regression analyses will be conducted considering additional co-factors (will be detailed in the statistical analysis plan).

Analysis of secondary efficacy endpoints

Secondary efficacy variables will be tested descriptively and in an exploratory manner.

1. Log transformed levels of Lactate dehydrogenase (LDH) at day 5 as a surrogate marker for organ damage

Log transformed levels of LDH will be analyzed using linear regression adjusted for baseline log levels of LDH, center and minimization factors.

95% confidence intervals will be additionally calculated.

Statistical procedures to check on a normal distributed of data, to be applied in case of non-normally distributed data, and to verify and handle minimization factors will be described in the statistical analysis plan, which will be finalized prior to unblinding.

2. 28-day mortality (all cause death)

The percentage of patients who have died at Day 28 will be presented by treatment group. Patients who will be discharged from hospital or early terminated before Day 28 will be considered having an event on the day of discharge or early termination, if a telephone interview was not possible and/or no information about alive/death status is known. The Chi-squared or Fisher's exact test will be used to compare proportions. 95% CIs will be additionally calculated. Logistic regression analyses will be conducted considering additional co-factors (will be detailed in the statistical analysis plan).

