Eligible patients will be centrally allocated using a dynamic randomization (1:1) at baseline (day 1) to Group A or B to receive the treatment or placebo. Dynamic randomization factors will be age in years (<65 years vs. ≥65 years), presence of at least one relevant co-morbid condition (hypertension, diabetes, coronary artery disease) for study protocol versions prior version 6.0 and center.

After screening at day -1 and randomization at day -1 or day 1, patients will be treated with APN01 or placebo intravenously twice daily (BID) every 12 hours (± 1 hour) over 3 to 30 minutes in the morning and in the evening until day 7 (14 doses). If a patient will be discharged from hospital before day 7 treatment can be stopped at day of discharge.

Periods and duration

The study will consist of three periods: screening (day -1), treatment period (day 1 to day 7) and follow-up period (day 10, day 14 and day 28). Study duration is up to 29 days per patient. Total study duration is up to 5 months, with 2-4 months recruitment period per country.

Number of patients planned

The planned sample size is 200 treated patients. Approximately 40 sites in Europe, Russia and US are planned, hence for a 1:1 (APN01:Placebo) randomization scheme. 186 patients (93 per group) will yield 80% power to detect a 20% absolute risk reduction in the primary composite endpoint, from 50% in the placebo group to 30% in the APN01 group at a two-sided alpha of 0.05. To consider patients who will be randomized but not treated a total of 200 patients (100 per group) will be enrolled.

DSMB Meetings

The regular DSMB will be performed after randomization of 8-10, 20, 50, 100 (if necessary), and 150 (if necessary) patients. Furthermore an ad hoc meeting of the DSMB may be called at any time by the DSMB Chair, coordinating investigator, medical monitor or sponsor imminent for any significant reason.

Study objectives

The primary study objective is to assess clinical efficacy of APN01 using a composite outcome of all cause-death or need of invasive mechanical ventilation up to 28 days.

The secondary study objectives are to assess efficacy of APN01 using log transformed levels of Lactate dehydrogenase (LDH) as a surrogate marker for organ damage, to evaluate the safety of APN01 in patients with severe COVID-19 and to monitor other biomarker changes (e.g. IL-6, Ang II) in patient with severe COVID-19 treated with APN01.

2 Efficacy and Safety Endpoints

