4.4.1 Analysis of Primary Efficacy Endpoint

The primary endpoint is a composite endpoint of all cause-death or invasive mechanical ventilation (up to 28 days or hospital discharge).

The following null hypothesis will be tested:

- $H_0: p_{APN01} = p_{Placebo}$

versus the alternative

- $H_1: p_{APN01} \neq p_{Placebo}$

H_0 will be tested using a Chi-squared test. The level of significance is 5% (two-sided). In addition, logistic regression analyses will be conducted considering additional co-factors.

All cause-death

The percentage of patients who have died at Day 28 will be presented by treatment group.

Patients with death from any cause will be used for this endpoint as part of responder. Patients who are still alive at Day 28 will be considered as non-event.

The following cases may occur:

- Patient discharged from hospital **and** discontinued before Day 28, will be followed up by telephone interview to check whether they are alive or dead, if unclear as no telephone interview available, death is assumed (worst case) at last available date of early termination, hospitalization or hospital discharge
- No discharge from hospital, **but** early discontinuation before Day 28 will be followed up by telephone interview to check whether they are alive or dead, if unclear as no telephone interview available, death is assumed (worst case) at date of early termination
- Discharged from hospital, **but** no discontinuation before Day 28: No telephone interview, but regular entry at Day 28 about alive/death status

Invasive mechanical ventilation (up to 28 days or hospital discharge)

Invasive mechanical ventilation is defined as patients who are intubated or have a tracheostomy tube and are receiving positive pressure ventilation. Patients with at least one invasive mechanical ventilation (event with type of ventilation 'Mechanical ventilation') up to 28 days or hospital discharge will be used for this endpoint as part of responder.

Chi-squared test

Proportion of responder, i.e. those patients that died or having an invasive mechanical ventilation (up to 28 days or hospital discharge), as well as the p-value (two-sided) will be reported.

Logistic regression

A logistic regression with the responder (yes/no) as independent variable will be applied.

The following co-factors will be included in the logistic regression:

- Arterial hypertension

- ❑ Diabetes
- ❑ Coronary artery disease
- ❑ Age (<65 years vs. >=65 years)
- ❑ Center

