The odds ratio along with its associated 95% confidence intervals will be reported.

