4.4.2 Analysis of Secondary Efficacy Endpoints

Log transformed levels of lactate dehydrogenase (LDH) at Day 5 as a surrogate marker for organ damage (powered secondary endpoint)

Results of LDH will be converted to standard unit before any calculation if needed. Conversion of all lab values will be described in a separate document 'Conversion_3570_VX-X_2020-MM-DD'. Standardized results will be log transformed for this endpoint.

Log transformed levels of LDH will be analyzed using linear regression adjusted for baseline log levels of LDH, center and age. 95% confidence intervals will be additionally calculated.

In protocol the wording of "minimization factors" is used: Stratification factors from the randomization are used in models as covariates.

Before application of the linear regression, it will be checked if the residuals are approximately normally distributed (QQ-Plot, Shapiro Wilk test). If there are no major violations of the normal distribution the model can be applied. If there are major violations available only descriptive analyses will be displayed.

Point estimate together with standard error and two-sided 95% confidence interval as well as p-value (two-sided) will be reported.

28-day mortality (all cause death)

The percentage of patients who have died at Day 28 will be presented by treatment group.

The following cases may occur:

- Patient discharged from hospital **and** discontinued before Day 28, will be followed up by telephone interview to check whether they are alive or dead, if unclear as no telephone interview available, death is assumed (worst case) at last available date of early termination, hospitalization or hospital discharge
- No discharge from hospital, **but** early discontinuation before Day 28 will be followed up by telephone interview to check whether they are alive or dead, if unclear as no telephone interview available, death is assumed (worst case) at date of early termination
- Discharged from hospital, **but** no discontinuation before Day 28: No telephone interview, but regular entry at Day 28 about alive/death status

Chi-squared test or Fisher's exact test

Proportion of responder, i.e. those patients that died, as well as the p-value (two-sided) will be reported.

Logistic regression

The following co-factors will be included in the logistic regression:

- ❑ Arterial hypertension
- ❑ Diabetes

- ❑ Coronary artery disease
- ❑ Age (<65 years vs. >=65 years)
- ❑ Center

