Separate models will be calculated for Day 7, 10, 14 and 28.

The odds ratio along with its associated 95% confidence intervals will be reported.

Time to death (all causes)

Time to death [days] = Date of death - Date of randomization.

Patients who will be alive at Day 28, or who will be discharged from hospital/early terminated before Day 28 will be censored at discharge/early termination if they cannot be reached at or after Day 28 by means of a telephone interview. Patients who will be reached at or after Day 28 by means of a telephone interview will be censored at the date of telephone contact if they are alive.

The following cases may occur:

- Patient discharged from hospital **and** discontinued before Day 28, will be followed up by telephone interview to check whether they are alive or dead, if unclear as no telephone interview available, death is assumed (worst case) at last available date of early termination, hospitalization or hospital discharge
- No discharge from hospital, **but** early discontinuation before Day 28 will be followed up by telephone interview to check whether they are alive or dead, if unclear as no telephone interview available, death is assumed (worst case) at date of early termination
- Discharged from hospital, **but** no discontinuation before Day 28: No telephone interview, but regular entry at Day 28 about alive/death status

Time to death (all causes) will be analyzed using Kaplan-Meier estimates and plots, log-rank test, and Cox proportional hazards model (adjusted for center and age to derive hazard ratios and corresponding 95% confidence intervals).

Kaplan-Meier estimates and Log-rank test

Kaplan-Meier table (product-limit “survival” estimates with 95%-CI, Standard error, Number of patient with event, Number of patient at risk) for Time to death [days], Kaplan-Meier Summaries of Event/Censoring (Number of patient with event, Number of patient censored, Total number of patients), Quartile Estimates (Median Time to Event, 1st Quartile, 3rd Quartile, 95%-CI) and Kaplan-Meier table (“survival” estimates with 95%-CI) for Timepoint (28 days). Time to death [days] will be displayed by a Kaplan-Meier-curve. Treatments groups will be compared with Log-rank test.

Cox proportional hazards model

The hazards ratio along with its associated 95% confidence intervals as well as parameter estimate and p-value (two-sided) will be reported.

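### Seven supportive logistic models adjust for Center without saying how; coded as fixed site indicators, they would overstate a non-null treatment odds ratio and understate its standard error

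*SAP*

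**What the plan says.** SAP 4.4.1 tests the primary composite with an unadjusted chi-squared test at two-sided 5%. From that test it reports the group proportions "as well as the p-value (two-sided) will be reported". It then adds a model: "In addition, logistic regression analyses will be conducted considering additional co-factors". The specification is "The following co-factors will be included in the logistic regression", followed by hypertension, diabetes, coronary disease, age split at 65, and Center. The output is: "The odds ratio along with its associated 95% confidence intervals will be reported".

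SAP 4.4.2 repeats the same list for 28-day mortality, for WHO-score response ("Separate models will be calculated for Day 7, 10, 14 and 28") and for any invasive mechanical ventilation.

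On size, SAP section 1 says "Approximately 40 sites in Europe, Russia and US are planned", for 200 patients.

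On form, the LDH paragraph of Protocol 8.7.1.2.5 promises that procedures "to verify and handle minimization factors will be described in the statistical analysis plan, which will be finalized prior to unblinding". The LDH paragraph of SAP 4.4.2 answers only that "Stratification factors from the randomization are used in models as covariates". SAP section 5 changes how age enters the models and is silent on Center. The minimum agenda for the blind data review in SAP 4.8 does not include pooling of centres. Appendix A, which SAP section 4 says describes the outputs, is not in the supplied text.

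**The concern.** Maximum likelihood with one indicator per small site is the classic sparse-strata problem. Each site intercept is estimated from a handful of patients, and the error does not average out of the treatment coefficient. A non-null log odds ratio is pushed away from 0, and the model standard error falls below the estimator's real spread. Sites where everyone or no one has the event contribute nothing.

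At stake is how the size of effect is read. For the primary endpoint, this odds ratio is the only effect estimate with a confidence interval described in the supplied SAP text. Benefit or harm would look larger than it is, with more certainty than the data support. Leaving the form open also leaves a choice between specifications that give different answers.

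**Working it through.** **The plan's own figure.** For 50% against 30%, two-sided 5%, 80% power, the number per arm is
[1.960·√(2·0.40·0.60) + 0.8416·√(0.50·0.50 + 0.30·0.70)]² / 0.20² = [1.3579 + 0.5708]² / 0.04 = 3.7199 / 0.04 = 93.0, so 186 in total. This reproduces the plan. Power with 100 per arm is 82.8%. Neither figure involves the logistic model.

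**Sparsity.**
- Models: 1 primary + 1 mortality + 4 WHO visits + 1 ventilation = 7.
- Patients per site: 200/40 = 5.
- Expected primary events at the design rates: 100 × 0.50 + 100 × 0.30 = 80.
- Parameters with fixed indicators: intercept 1 + treatment 1 + comorbidities 3 + age 1 + centre 39 = 45; if 33 sites enrol, 6 + 32 = 38.

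**Simulation of the fixed-indicator model.** The assumed true odds ratio is (0.30/0.70)/(0.50/0.50) = 0.429, conditional on covariates and site. Intervals are Wald: log OR ± 1.96 SE. Site standard deviation on the logit scale is 0.5. Co-factor prevalences and effects, site heterogeneity and accrual patterns are assumptions, since the documents do not give them.
- Setting A: 4,000 trials per scenario, biased-coin minimisation (probability 0.8, assumed) on centre and age group.
- Setting B: 1,500 to 3,000 trials per scenario, arms balanced within centre, different covariate assumptions.

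Shift = ln(median OR)/ln(0.429) − 1. Where A gives only the shift, OR = 0.429^(1 + shift).

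| Planned sites, accrual | A: median OR (shift), coverage | B: median OR (shift), coverage |
|---|---|---|
| 40, uneven (A: about 33 enrol) | 0.36 (+20%), 90% | 0.358 (+21%), 89.9% |
| 40, more uneven (about 28 enrol) | 0.37 (+17%), 91–92% | not run |
| 40, equal | 0.32 (+34%), 85% | 0.325 (+33%), 84.7% |
| 20, uneven (about 18 enrol) | 0.38 (+13%), 92% | not run |
| 20, equal | 0.37 (+16%), 92% | 0.380 (+14%), 91.4% |
| 16, uneven (about 15 enrol) | 0.40 (+9%), 93% | not run |
| 16, equal | 0.38 (+13%), 93% | 0.386 (+12%), 92.4% |
| 10, equal | not run | 0.398 (+9%), 93.9% |

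Monte Carlo error in A is about 0.5 points for coverage and 1 point for the shift. A repeat of B with 40 equal sites gave 0.326 and 86.9%.

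**Where it comes from.** In A the same model without Center shifts by −3 to −1%, with coverage 94–96%. The shift at 40 uneven sites is +20 to +21% for site standard deviations from 0 to 1.0, so it does not depend on real site differences.

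**Standard error and width (B, 40 uneven).** Mean model SE 0.361 against empirical SD 0.415: ratio 0.87. Log-scale interval width is 1.41 with centre indicators and 1.22 without. The bias is |ln 0.358 − ln 0.429| / 0.361 = 0.18/0.36, or 0.5 of a standard error.

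**Other truths.**
- True OR 1: no directional bias. Intervals miss in 7.0% (A, 40 uneven), 8.7% (A, 40 equal) and 7.7–7.9% (B, 40 sites), so coverage is mostly 92–93% and 91.3% at worst.
- Harm, OR 2.33 (A, 40 uneven): median 2.77, coverage 91–92%.
- 28-day mortality (A, 40 uneven): +22%, 91% if placebo risk is 33% (the overall death proportion in the UK cohort in Protocol 6.1, used as an assumption); +27%, 93% if 15% (assumption). With 16 uneven sites: +11%, 93% and +13%, 95%.

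**Alternatives on the same data (A).**
- Random centre intercept: +1 to +4%, coverage 94–95%, null rejection 5.1–5.5%.
- Conditional logistic by centre: +2 to +5%, coverage 94–95%, null rejection 5.5–5.7%.

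In B (40 equal), a penalised approximation to the random intercept gave 0.425 with 94.5%, and conditional logistic 0.413 with 93.9%. At site standard deviation 1.0 the approximation erred slightly toward 1 (0.451, coverage 96.0%).

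**The case against.** The strongest reply is that no decision rests on these models. The primary test is unadjusted, the secondary endpoints are exploratory under Protocol 8.7.1.2.5, and the logistic output is an odds ratio with an interval, not a p-value. The 7 to 9% null miss rate is therefore not the size of any planned test. Both primary proportions are reported, so a reader can derive a risk difference. For the six secondary models the protocol also plans 95% intervals beside the test of proportions, which SAP section 5 does not withdraw. All of this stands and limits the severity.

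Four further points stand as limits:
- **The form is inferred.** A reader might conclude that the SAP prescribes fixed indicators. It does not; it says only that the factors are covariates. Reading the reported odds ratio as the treatment effect is also inferred, because SAP 4.4.1 calls the responder the independent variable and does not list treatment.
- **Too narrow is relative.** A reader might infer that adjusting for Center shrinks the interval. It widens it. The interval is short only against that estimator's own variability, and part of the undercoverage comes from the shifted estimate.
- **Enrolling sites are unknown.** About 40 is a plan. The equal-accrual case is an upper bound, and at 10 sites the effect is small.
- **The simulated truth is not exactly the design.** A conditional odds ratio of 0.43 with 50% placebo risk gives an active-arm risk of about 31.5% (site standard deviation 0.5) or 33.5% (1.0), not 30%. The conditional odds ratio that gives 30% would be about 0.40 or 0.35.

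What does not stand is that this is only missing detail. Coding the list as written, in the usual way, produces the distortion.

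**Conclusion.** The point holds for supportive estimates: minor to moderate. If Center is fitted as fixed indicators, a true conditional odds ratio of 0.43 would typically be reported as about 0.36 with about 90% coverage at 40 unevenly accruing sites. It would be about 0.32 to 0.33 with about 85% if all 40 enrol equally, and about 0.38 to 0.40 with 92 to 94% at 16 to 20 sites (single settings run from 0.37 and 91.4%). With a true odds ratio of 1 there is no bias, only mild undercoverage.

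This rests on the fixed-indicator reading, the treatment reading of the odds ratio, and assumed covariates, site heterogeneity and accrual. The WHO-response and ventilation models were not simulated, so no size is claimed for them. A reader might infer that the trial's type I error or primary conclusion is compromised. The documents do not support that, because the confirmatory chi-squared test and the sample size do not use Center.

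**What to change.** Before unblinding, state in SAP 4.4.1 and 4.4.2 that each logistic model has response as the dependent variable, treatment as a factor, the listed co-factors and a random centre intercept. Name conditional logistic regression stratified by centre as the fallback on non-convergence. Optionally, report the unadjusted primary risk difference with a 95% interval beside the chi-squared p-value; a Newcombe interval covered 95–96% in the simulations, with width 0.26–0.27.

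The cost is SAP wording and a few program lines, with no new data. The fallback is slightly less precise (76% against 80% rejection for the random intercept at 40 uneven sites and odds ratio 0.43) and uses no information from sites where all or no patients have the event.

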8.3.3.1 Withdrawal of Patients from the Clinical Trial

The following circumstances may lead to discontinuation of the study by an individual patient who will then be recorded as a drop-out, include but are not limited to the following:

- Withdrawal for personal reasons
- AEs necessitating withdrawal from the clinical trial
- Occurrence of a severe adverse reaction (SAR)
- Sudden incidence of diseases
- Circumstances in which the health of the patient would be endangered upon continued participation in the clinical trial
- Lost to follow-up
- Other (must be specified)

If a patient withdraws from the study at any time either at his or her request or at the investigator's discretion, an "End-of-Study/Early Termination" visit should be performed and the "End of Study" eCRF section should be used to collect the relevant information. The visit may also be performed as a phone visit or in-home visit (in Russia). The reason(s) for withdrawal must be recorded on the relevant page of the patient's eCRF and the patient's source data. Patients discharged from hospital before day 28 will be contacted by telephone to assess if they are alive at day 28.

It is vital to obtain follow-up data for any patient withdrawn from the study because of an AE. Every effort must be made to undertake protocol-specific safety follow-up procedures. If a patient is discontinued due to an AE, the event should be followed up until resolution or until the event becomes chronic.

The Data Safety Monitoring Board may also recommend withdrawal of patients.

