8.3.3.2 Premature Treatment Discontinuation

Patients must stop the IMP if the patient experiences any kind of hypersensitivity reaction. The patient may remain in the study and continue to attend study visits.

Patients may be withdrawn from the IMP after initiation of infusion if in the opinion of the investigator or of the Medical Monitor there is a risk to the patient's safety if they further receive IMP. If the patients are withdrawn from IMP, they may remain in the study and continue to attend study visits.

IMP treatment can be stopped early if a patient will be discharged before day 7.

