8.4.8.3 Early Termination

All enrolled patients who discontinue early, or withdraw from the clinical trial will have the follow-up assessments and procedures completed for their safety as outlined in Table 1. Patients who discontinue early or withdraw from the clinical trial will not be replaced as long as 200 patients complete the study according to the protocol.

In some cases, it may be necessary for patients to return to the study site or will be contacted for a phone visit or in-home visit (in Russia) for additional care, confinement, and/or follow-up. Circumstances in which this may be necessary are:

- Follow-up on abnormal laboratory evaluations
- Follow-up on an ongoing AE at the final visit (day 28) and or final phone visit

All additional safety follow-up visits will be at the discretion of the investigator, the PI and the Sponsor.

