8.7.1.2.4 Statistical Analysis

Continuous variables will be summarized with means, standard deviations, medians, lower and upper quartiles, minimums and maximums. Frequencies and percentages will be used to summarize categorical variables.

For time-to-event analyses censoring information will be used.

It is assumed that no patients will discontinue the study early prior to day 28 or hospital discharge in this Covid-19 setting. It is also assumed, that only very few missing values will arise due to not done evaluations. No imputation of missing values (e.g., no last observation carried forward (LOCF)) is planned, unless stated otherwise.

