8.7.2 Determination of Sample Size

186 patients (93 per group) will yield 80% power to detect a 20% absolute risk reduction in the primary composite endpoint, from 50% in the placebo group to 30% in the APN01 group at a two-sided alpha of 0.05 when applying a two group Chi-Squares test. To consider patients who will be randomized but not treated a total of 200 patients (100 per group) will be enrolled.

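### For a patient who leaves the study while still in hospital, the plan asks whether the patient is alive but does not require later invasive ventilation to be obtained, and unknown ventilation in effect counts as no primary event.

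*SAP*

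**What the plan says.** **Leaving the study versus stopping treatment.** Protocol 8.3.3.1 lists adverse events, a severe adverse reaction and sudden illness among the circumstances that may make a patient a drop-out. Protocol 8.3.3.2 deals with stopping the drug alone: "If the patients are withdrawn from IMP, they may remain in the study and continue to attend study visits".

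**Contact after exit.** For discharged patients, Protocol 8.3.3.1 says: "Patients discharged from hospital before day 28 will be contacted by telephone to assess if they are alive at day 28". For patients still in hospital at exit, SAP 4.4.1 says that "early discontinuation before Day 28 will be followed up by telephone interview to check whether they are alive or dead". If no interview is available and status is unclear, the SAP assumes death at the exit date; Protocol 8.7.1.2.5 likewise counts unknown vital status as an event. Protocol 8.4.8.3 adds: "All enrolled patients who discontinue early, or withdraw from the clinical trial will have the follow-up assessments and procedures completed for their safety", with reference to Table 1.

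**Scoring.** Under the death component, SAP 4.4.1 says: "Patients who are still alive at Day 28 will be considered as non-event". The ventilation component needs at least one recorded event of the mechanical ventilation type, up to Day 28 or discharge. The primary set is all randomized patients (SAP 3.1, 3.4), and SAP 4.7 allows no imputation of missing values.

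**Expected withdrawals.** Protocol 8.7.1.2.4: "It is assumed that no patients will discontinue the study early prior to day 28 or hospital discharge".

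**The concern.** A patient who is discharged has closed the ventilation window. A patient who leaves the study from a hospital bed has not: that patient can be intubated the next day, and the event lies within the endpoint's own definition. The only contact that the SAP prescribes for this patient's primary outcome establishes survival.

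The two components are then handled in opposite ways when information is lacking. Unknown vital status is worst case. Unknown ventilation is in effect best case, because no record means no event.

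This matters most if leaving the study is related to treatment. An adverse reaction may end participation, so APN01 could have more in-hospital leavers. Unrecorded intubations among those who survive would then lower the APN01 event rate in the only confirmatory test. The secondary endpoint of any invasive ventilation would be affected in the same way.

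**Working it through.** **1. The plan's own figure.** Inputs from Protocol 8.7.2: "from 50% in the placebo group to 30% in the APN01 group at a two-sided alpha of 0.05", 80% power, 1:1 allocation, Chi-squared test. With p1 = 0.50, p2 = 0.30 and mean p = 0.40:

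n = [1.960 × √(2 × 0.40 × 0.60) + 0.842 × √(0.50 × 0.50 + 0.30 × 0.70)]² / 0.20² = 93.0 per group.

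This reproduces 93 per group (186 in total). With the 100 per group to be enrolled, power is 82.8%. The increase from 186 to 200 is for patients randomized but not treated; nothing is set aside for study withdrawal.

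**2. Tracing one patient through the rules.** The patient leaves the study in hospital on Day 3, is intubated on Day 5, is extubated, and is alive at Day 28.
- *Death component:* the call finds the patient alive, so no event.
- *Ventilation component:* an event if the Day 5 intubation is on record, otherwise none.
- *Must it be on record?* Table 1 has no ventilation row. At a Day 28 phone visit, footnote 17 waives the respiratory and patient-status assessments. The WHO scale is not waived, and its scores 7-9 mean mechanical ventilation, but it describes the state when assessed, and the SAP does not feed it into the primary endpoint.
- *Other rules:* the ventilator-free-days rule in SAP 4.4.2 foresees ventilation starting after discontinuation but counts duration only to discontinuation. Time to first ventilation is censored at discontinuation. Neither says whether such ventilation counts in the primary endpoint.

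**3. Size under assumed rates.** The documents supply no withdrawal rate and no rate of later intubation, so both are assumptions.

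Missed events per 100 = in-hospital leavers with known survival × share later intubated, unrecorded and alive at Day 28.

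| Leavers per 100 | Share 20% | Share 40% |
|---|---|---|
| APN01, 8 | 1.6 | 3.2 |
| Placebo, 3 | 0.6 | 1.2 |
| Difference | 1.0 point | 2.0 points |
| 5 in each arm | 1 per arm | 2 per arm |

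**4. Effect on the test.** Exact binomial enumeration of the uncorrected Chi-squared test, 100 per group, true rate 50% in both arms:

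| Observed rates, APN01 vs placebo | Two-sided rejection | Rejection in favour of APN01 |
|---|---|---|
| 50.0% vs 50.0% (nothing missed) | 5.6% | 2.8% |
| 48.4% vs 49.4% (1.0 point) | 5.8% | 3.8% |
| 46.8% vs 48.8% (2.0 points) | 6.6% | 5.2% |

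A wider range, with withdrawal on APN01 only (spurious benefit = 0.50 × share withdrawn × share of their events missed):
- 2% withdrawn, 25% missed: 0.25 points, two-sided rejection 5.6%.
- 5% withdrawn, 50% missed: 1.25 points, 6.0%.
- 10% withdrawn, 75% missed: 3.75 points, 9.1%.

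**5. Equal withdrawal, true 50% vs 30%.** If the same share of events is lost in both arms, power falls from 82.8% to 81.2% (5% withdrawn, half missed), 79.5% (10%, half) or 77.8% (10%, three quarters). If instead the same number is lost (1-2 per arm), the difference stays at 20 points and power barely moves (83.1-83.5%). Both event rates are understated either way.

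**6. Near the boundary.** With 50 of 100 events on placebo, 37 on APN01 gives p = 0.064 and 36 gives p = 0.046. One unrecorded event can change the conclusion.

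**The case against.** The strongest case against is that follow-up after exit is more than one telephone question.
- Protocol 8.3.3.1 asks for an early termination visit and stresses follow-up of patients withdrawn for an adverse event. Protocol 8.4.8.3 sends early leavers to Table 1. Protocol 8.5.2.2.13.1 follows adverse events even after participation has ended.
- SAP section 4 lists a separate early-termination visit at Day 28. At Day 28 neither the WHO scale nor adverse-event recording is waived for a phone visit.
- The ventilation component of SAP 4.4.1 is not cut off at study exit, so a recorded later intubation could still count.

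All of this stands. A reader might infer that such patients are only ever asked whether they are alive, and that later intubation is necessarily missed; these provisions do not support that. A reader might also take the sentence that makes survivors non-events as overriding a ventilation event. It sits under the death component and does not. What the provisions do not do is require ventilation between exit and Day 28 to be obtained. A Day 28 WHO score can miss an intubation that has ended.

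A reader might also infer a bias that always favours APN01. That does not follow either. It needs more in-hospital leavers with known survival on APN01, while leavers with unknown vital status are counted as events and push the other way.

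Finally, the rates in the working are assumed, and at moderate values the effect on the test is small. That is correct.

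**Conclusion.** There is a real gap in outcome ascertainment and classification for one group: patients who leave the study before discharge and are known to be alive. Their ventilation status need not be obtained, and if it is unknown they default to non-events, opposite to the plan's rule for unknown vital status.

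The size cannot be read from the documents, which assume no early discontinuation. Under the assumed 8 versus 3 leavers per 100, with 20-40% later intubated, unrecorded and alive, the spurious benefit is 1-2 percentage points, and false wins for APN01 rise from 2.8% to 3.8-5.2%. With equal withdrawal both event rates are understated, and power falls slightly if events are lost in proportion. The net direction is not certain. The effect is likely to be modest, but it touches the only confirmatory test and is cheap to close, so the change should be made.

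**What to change.** 1. **Ascertainment.** In Protocol 8.3.3.1 and SAP 4.4.1, have the Day 28 contact, or the hospital record where consent allows, record any invasive ventilation with its start date, and the hospital discharge date, for every patient who left early. State that ventilation up to Day 28 or discharge counts as a primary event even if it began after study exit.
2. **Classification.** If ventilation status remains unknown for a patient who left in hospital, keep the patient in the FAS and count an event, in line with the worst-case rule for vital status. Add a sensitivity analysis counting these patients as non-events. Setting the endpoint to missing would be worse, because it would drop randomized patients from the primary test.
3. **Separate steps.** Reconcile Protocol 8.3.3.1 and 8.3.3.2 so that ending study drug and ending follow-up are recorded as distinct steps. This concerns data collection only and leaves unchanged when dosing stops.

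The cost is two extra questions in a contact already planned, short wording changes and one sensitivity table. The downside is that a few patients are classified conservatively, which works against whichever arm has more of them; the sensitivity analysis shows by how much.
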